## q. Intention to treat analysis:

After randomization, some patient may become non complaint to the allocated treatment and will be lost to follow-up. Randomization is a key process in a randomized controlled trial. So exclusion of this non complaint and drop out patients from the analysis of the result may create bias, reduce the sample size and thereby reduce the power of statistical tests and increase the probability of type II error.

Treatment group and control group will be analyzed with respect of their random allocation regardless of what will happen subsequently (whether they will actually receive the treatment or not).

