#### **ABSTRACT**

**Background:** Irritable Bowel Syndrome (IBS) is a common functional gastrointestinal disorder. Common clinical manifestation include abdominal pain, bloating, altered bowel habit which bears a great impact on the quality of life of an individual. Previously limited number of studies carried out in our country to assess the effect of probiotics on IBS patients which yielded mixed results. Further study preferably with larger sample and longer duration was recommended. Aims and objectives: This study aims to see the effect of probiotics on IBS.

Material and method: This is a controlled randomized clinical trial. The patient will be selected on the basis of Rome III criteria. IBS patients with a sample size of 400 will be taken. Purposive non probability method of sampling will be employed. In this method the patients who will be readily available and in close proximity will be selected according to the selection criteria. Patient will be collected from gastroenterology outpatient department. After full explanation of the study procedure, informed written consent will be taken. Participants will be randomized to receive either probiotics (Biocult®, Sandooz Bd. Ltd.) with standard treatment or only standard treatment for 8 weeks. All participants will be interviewed with baseline symptom score. Similar interview for symptom score will take place at 1 month interval for 3 times (including 1 month post treatment). All data will be processed by the SPSS program values will be expressed as frequencies or mean±SD unless otherwise mentioned. Between groups analysis will be done by Chi-square test, unpaired or paired students t-test as applicable; while predictive values will be seen by regression analysis. Only P values <0.05 will be considered as significant.

**Result:** This study will see the effect of two months use of probiotics on IBS and thereby highlight over the longer treatment of IBS.

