## Adjustment for non-compliance/cross-over

We also need to consider dropouts and poor adherence in calculating the sample size. It is estimated that around 5%-8% patients in both groups will drop out in different stages of the trial. The adjusted sample size is calculated based on the following formula –

Adjusted sample size,  $n_{adj} = n/(1-c_1-c_2)^2$ 

Here, n = 270

 $c_1$  = Dropout rate in control group = 8%

c2= Dropout rate in control group = 8%

Adjusted sample size,  $n_{adj} = 270 / (1 - .08 - .08)^2$ 

 $= 384 \approx 400$ 

The adjusted sample size in each group = 200

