## p. Procedure of data analysis and interpretation:

Data will be analyzed using computer based SPSS program (version 13.0). All data will be expressed as frequencies and mean ( $\pm$ SD or  $\pm$  SE). Comparison of symptom score between subgroups will be done by Student's unpaired t-test. Pearson's correlation test will be used to see correlation among different variables. P values less than or equal to 0.05 will be considered as significant.

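### Section q wants dropouts kept in the analysis, but the unpaired t-test named in section p leaves out anyone without a score unless scores are imputed, and the protocol does not provide for that

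*Protocol*

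**What the plan says.** Section q (Intention to treat analysis) foresees that "some patient may become non complaint to the allocated treatment and will be lost to follow-up". It argues against leaving such patients out: "So exclusion of this non complaint and drop out patients from the analysis of the result may create bias", with a smaller sample, lower power and more type II error as further consequences. Its rule is "Treatment group and control group will be analyzed with respect of their random allocation regardless of what will happen subsequently".

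Section p (Procedure of data analysis and interpretation) names the method: "Comparison of symptom score between subgroups will be done by Student's unpaired t-test". It mentions no visit, no analysis set and no treatment of missing scores. The Abstract adds other tests: "Between groups analysis will be done by Chi-square test, unpaired or paired students t-test as applicable", and regression for predictive values.

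The sample size section (Adjustment for non-compliance/cross-over) gives the expected loss: "It is estimated that around 5%-8% patients in both groups will drop out in different stages of the trial". Scores are collected at baseline and at months 1, 2 and 3, the last being one month after the 8 weeks of treatment. Under Outcome variables, a responder is a patient whose pain score improves by at least 30% on baseline, so that status also needs a follow-up score.

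**The concern.** The protocol sets a principle about dropouts and, one section earlier, names a method that does not deliver it. A two-sample t-test on collected scores has no place for a patient with no score at that visit. Followed literally, section p makes the omission that section q warns about, and the result would still be reported as intention-to-treat.

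What is at stake is the comparability that randomisation creates. If the patients who leave one arm differ from those who leave the other, the t-test compares two selected groups. A t-test at month 2 also makes no use of the month-1 score of a patient who left in between, although that score says something about how the patient was doing.

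**Working it through.** **Inputs from the protocol.** SD 87.77 (IBS-SSS) and difference 30, entered in the formula as points (section i); Z values 1.96 and 0.84 (section i); dropout 5%-8%, with 8% used for each arm, and 200 per arm (Adjustment for non-compliance/cross-over).

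**1. The plan's own figures.**
- Per arm: 2 × 87.77² × (0.84 + 1.96)² / 30² = 134.2, rounded up to 135; total 270. This agrees.
- Inflated total: 270 / (1 − 0.08 − 0.08)² = 382.7, or 191.3 per arm. Rounded up to 192 per arm this is the stated 384, taken to 400.

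The squared form of this inflation is the one used when all randomised patients stay in the analysis and non-adherence dilutes the effect. Allowing only for lost patients would give 270 / 0.92 = 293.5, or 294 in total. So the sample size section, like section q, fits an analysis that keeps the dropouts.

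**2. Patients affected.**
- 5%: 0.05 × 200 = 10 per arm, 20 in all.
- 8%: 0.08 × 200 = 16 per arm, 32 in all.

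These are upper figures for month 2. The protocol spreads dropout over different stages, and follow-up runs to month 3, so some of these patients will have a month-2 score.

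**3. Power.** Power = Φ(30 / (87.77 × √(2/n)) − 1.96), with n scored patients per arm.

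| Dropout | n per arm | Power |
|---|---|---|
| 0% | 200 | 92.8% |
| 5% | 190 | 91.5% |
| 8% | 184 | 90.6% |

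Power stays well above the planned 80%.

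**4. Bias in the score comparison.** Let d be the dropout proportion in an arm and g the difference, in SD units, between the unseen mean of its dropouts and the mean of its completers. The all-patient mean is the completer mean plus d × g × SD. The completer comparison is therefore off by |d₁g₁ − d₂g₂| × SD. The protocol gives no value for g, so these rows are assumptions, with d = 8% in both arms.

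| Assumed g (arm 1, arm 2) | Calculation | Bias |
|---|---|---|
| 0.5, 0.5 | (0.04 − 0.04) × 87.77 | 0 points |
| 0.5, 0 | 0.04 × 87.77 | 3.5 points |
| 0.5, −0.5 | 0.08 × 87.77 | 7.0 points |

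At 5% dropout the last two rows become 0.025 × 87.77 = 2.2 and 0.05 × 87.77 = 4.4 points. The yardstick is the 30-point design difference.

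**5. The other named tests.** A chi-square test on responder status, a paired t-test of change and a regression on follow-up score each need the missing score too. None keeps the patient without a further rule.

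**The case against.** The strongest reply is that section p names a test, not an analysis set. It nowhere says that dropouts are excluded, and an unpaired t-test on imputed scores would satisfy both sections. A rule for missing scores is also commonly left to the statistical analysis plan, which is not at hand. The first part stands: a reader might infer that sections p and q contradict each other outright, or that the protocol excludes dropouts, and the text supports neither. The second part stands for the missing rule taken alone. What remains is that the protocol itself fixes a method which, run on the collected data, does not do what its next section requires.

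Other stronger readings also fail:
- The t-test is the only comparison named in section p, but not in the whole protocol, since the Abstract adds others.
- Non-compliant patients who attend their interviews stay in the t-test. Only patients without a score are affected.
- Month-1 scores of later dropouts are not necessarily lost altogether. They would count in a month-1 comparison and go unused only in later ones.
- At 8% dropout, the all-patient responder difference is 0.92 × (observed difference) + 0.08 × (difference among the missing), so it can lie 8 percentage points either side of the shrunken value. That extreme needs every missing patient to respond in one arm and none in the other, and it concerns a proportion, not the score that the t-test compares. It is no estimate of bias.
- A reader might suppose that patients who do not improve leave more often, or that the arms lose different patients. The protocol says neither, and assumes 8% dropout in both arms.

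**Conclusion.** The concern holds as a mismatch between the stated reason for intention-to-treat and the named method. At the protocol's own dropout it touches at most 10 to 16 of 200 patients per arm and costs about two points of power at most. The exposure is bias: none if dropouts differ from completers equally in both arms, and roughly 3.5 to 7 points on the IBS-SSS under the assumed 0.5 SD differences at 8% dropout. That would not overturn a true 30-point effect, but it is up to about a quarter of it (7.0 / 30 = 23%). The size rests on the assumed values of g, on the 8% figure and on SD 87.77 applying in this trial. The change is worth making because it is cheap and uses scores already planned.

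**What to change.** In section p, replace the unpaired t-test with a repeated-measures mixed model of the scores at baseline and months 1, 2 and 3. Put baseline in the outcome vector, so that all randomised patients are included and baseline is adjusted for. Report the end-of-treatment (month 2) contrast between the arms. Multiple imputation with baseline as a covariate is an acceptable alternative. Do not restrict the model to patients with a post-baseline score: anyone who left before month 1 would again be omitted, which is the exclusion that section q argues against.

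For the 30% pain-responder comparison, keep all randomised patients by counting a missing month-2 score as non-response, and add a best/worst-case range as a sensitivity analysis.

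The cost is revised analysis wording and a little more programming; no visit or measurement is added. Responder rates will be slightly lower in both arms: with 8% missing, each becomes 0.92 times the rate among patients with a score. The mixed model and multiple imputation, as usually applied, assume that missingness depends only on observed data, which should be stated.

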#### r. Time table:

(Activities with time schedule)

Topic selection: 03 month (Sept-Nov, 2014)

Literature search: All through the study period

Protocol writing and approval: 03 months (Dec-Feb, 2014)

Data collection: 12 months (Apr., 2015 –Mar., 2016)

Data analysis: 01 month (April, 2016)

Thesis writing: 02 months (March-April, 2016)

Revision, binding and submission: 02 months (May-June, 2016)

# s. Good clinical practice:

According to the principles of GCP developed by International Conference on Harmonisation (ICH) following principles will be ensured in this study -

- Data and reported results of clinical investigations are credible and accurate, and
- Rights, safety and confidentiality of participants in clinical research are respected and protected (Guidance for Implementation. WHO, 2002).

#### **Ethical Consideration:**

- a) Before starting this study, the research protocol was submitted and approved by the Ethical Review Committee of BSMMU, Dhaka.
- b) All participants will be informed about the objectives, methodology and purpose of the study in an easy understandable way.
- c) All information regarding benefits and hazards will be delivered to the all participants & those who agree to participate will be included in the study.
- d) Verbal and written consents will be taken from all participants without any influences prior to sample collection.
- e) If the participants have any question or any other problems, they will be requested to contact.
- f) Data obtained from the study will be used only for the research purpose and the confidentiality of all study information will be maintained strictly.
- g) Participants can withdraw themselves from the study any time even after giving consent.

# APPENDIX - I

# **DATA COLLECTION SHEET**

1. Ba	seline demograp	hic pro	ofile of t	he patients:	:		Date:
a)	Group	:					
b)	Patients ID no.	:					
c)	Name	:					
d)	Age	:					
e)	Sex	:					
f)	Religion	:					
g)	Occupation	:					
h)	Address	:					
i)	Contact no.	:					
Symp	otom severity sco	ore que	stionnai	ire:			
1. a)	Do you currentl	y suffe	from at	odominal pa	in?		
	Before treatm	ent	At 1	st month		At 2 nd month	At 3 rd month
	□Yes/□No			es/□No		□Yes/□No	□Yes/□No
b	) If yes, how seve	ere is v	our abdo	minal pain?			
	%			 			1000/
_		t very s	severe	Quite se	ve	re Severe	Very severe
	Before treatm	ent	At 1	st month		At 2 nd month	At 3 rd month
c	) Please enter the	numbe	r of day	s that you go	et t	he pain in every 10 da	ys.
	Before treatm	ent	At 1	st month		At 2 nd month	At 3 rd month
2	D		6	L 4 1 1°	_4 -	anian (hlastina era II	4:-14)9
2. a	) Do you current	y suffe	r Irom al	odominal di	ste	nsion (bloating, swoll	en or tight)?
	Before treatme	ent	At 1	st month		At 2 nd month	At 3 rd month
	¬Ves/¬No			es/¬No		□Ves/□No	¬Vec/¬No

6. In the following questions you may circle more than one answer:

Are your motions ever:

	Before treatment	At 1st month		
a)	Normal:	a)	Normal:	
b)	Hard:	b)	Hard:	
c)	Very thin (like string):	c)	Very thin (like string):	
d)	In small pieces (like rabbit pellets):	d)	In small pieces (like rabbit pellets):	
e)	Musky (like porridge):	e)	Musky (like porridge):	
f)	Watery:	f)	Watery:	
At	At 2nd month		At 3rd month	
a)	Normal:	a)	Normal:	
b)	Hard:	b)	Hard:	
		c)	Very thin (like string):	
c)	Very thin (like string):	d)	In small pieces (like rabbit pellets):	
d)	In small pieces (like rabbit pellets):	e)	Musky (like porridge):	
e)	Musky (like porridge):	f)	Watery:	
f)	Watery:			

7. In the following questions you may circle more than one answer:

Do you ever:

		Before	At 1st	At 2 nd	At 3 rd
		treatment	month	month	month
a)	Pass mucus (or slime or jelly) with your motions.	□Yes/□No	□Yes/□No	□Yes/□No	□Yes/□No
b)	Pass blood with your motion	□Yes/□No	□Yes/□No	□Yes/□No	□Yes/□No
c)	Have to hurry/rush to the toilet to open your bowels	□Yes/□No	□Yes/□No	□Yes/□No	□Yes/□No
d)	Strain to open your bowels	□Yes/□No	□Yes/□No	□Yes/□No	□Yes/□No
e)	Feel you haven't emptied your bowel completely after your have passed a motion	□Yes/□No	□Yes/□No	□Yes/□No	□Yes/□No

# 8. Do you ever:

a) Notice your stools are more frequent or loose when you get pain..

Before treatment	At 1st month	At 2 nd month	At 3 rd month
□Yes/□No	□Yes/□No	□Yes/□No	□Yes/□No

b) Notice whether the pain is frequently eased by opening your bowels.

Before treatment	At 1st month	At 2 nd month	At 3 rd month	
□Yes/□No	□Yes/□No	□Yes/□No	□Yes/□No	

9. In the last year on approximately how many weeks were you:		
	a) Absent from work due to IBS	
	b) At work suffering from IBS
